7.6.1.3 Multivariable Analysis

Cox proportional hazards regression will be used to identify factors associated with initiation of oxygen therapy. Covariates included in the adjusted model will be determined based on statistical significance and clinical rationale. Baseline covariates may include:

- Demographic characteristics: index year, age group, gender, race/ethnicity, insurance type, geographic region
- Baseline clinical characteristics: all-cause HCRU, all-cause health care costs, medication use, respiratory disease, Quan-Charlson comorbidity score, AHRQ comorbid conditions, smoking, provider specialty, pulmonary rehabilitation

Following standard procedures, regression diagnostics will be performed for each model to assess goodness of fit and violations of model assumptions (e.g. multicollinearity, non-proportionality). Violations of the model assumptions will be documented, and appropriate corrections will be made to the analysis.

Hazard ratios and associated 95% CIs and p-values will be reported for all covariates in the model.

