7.3.5.2 Clinical Characteristics

- **Underlying ILD type**—Patients will be classified into the following underlying ILD types based on claims from the entire study period: autoimmune ILD, HP, sarcoidosis, unclassified ILD/IIP, and multiple. The underlying ILD type will be defined based on the presence of ≥ 1 specific ICD-10-CM diagnosis code for autoimmune ILD, HP, and sarcoidosis. Patients without any underlying ILD diagnosis will be classified into the unclassified ILD/IIP type. Patients with diagnoses for >1 underlying ILD types will be classified as multiple.
- **Respiratory diseases**—Separate indicator variables will be created for the presence of ≥ 1 diagnosis code in any position on a medical claim. The following conditions will be included: pulmonary hypertension, acute respiratory failure, asthma, COPD, pneumonia, lung transplantation, upper respiratory tract infection, lower respiratory tract infection, lung cancer, and cystic fibrosis.
- **Other clinical characteristics** – Similar to respiratory disease, a separate indicator variables will be created for the presence of ≥ 1 diagnosis code in any position on a medical claim. The following conditions will be included: gastroesophageal reflux disease (GERD), heart failure, and obstructive sleep apnea.
- **Quan-Charlson comorbidity score**—A comorbidity score will be calculated based on the presence of diagnosis codes on medical claims.^{10, 11} The Quan-Charlson comorbidity score will also be categorized into the following groups: zero, one to two, three to four, and five or more.
- **Comorbid conditions**—General comorbid conditions will be defined using the Clinical Classifications Software managed by the Agency for Healthcare Research and Quality (AHRQ).¹² This measure generates indicator variables for specific disease

conditions based on ICD-9-CM and ICD-10-CM diagnoses. The top 20 comorbid conditions will be presented.

[figure not shown]
- **Smoking**—An indicator variable will be created to identify patients with evidence of current or prior tobacco use based on diagnosis codes or pharmacy fills for smoking cessation treatments (bupropion, varenicline tartrate, or nicotine [inhalation, gum, lozenge, transdermal]).
- **Pulmonary rehabilitation**—Indicator and count variables will be created for the presence of procedure codes for pulmonary rehabilitation.

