7.4 DATA SOURCES

Figure 3. Optum Data Ecosystem

Optum's Clinical EHR Database aggregates extensive clinical encounter data from a network of 140,000+ providers at more than 700 hospitals and 7,000+ clinics. The Clinical EHR Database currently has more than 104 million unique patients across the United States, with an average of 45 months of observed data per patient.

The Clinical EHR Database is robust, longitudinally linked, compliant with the Health Information Portability and Accountability Act of 1996 (HIPAA), and statistically de-identified. Data elements include demographics; medications prescribed and administered; immunizations; allergies; lab results (including microbiology); vital signs and other observable measurements; clinical and inpatient stay administrative data; and coded diagnoses and procedures.

Optum's Clinical EHR Database can deliver a longitudinal record that covers a comprehensive spectrum of patient health, medical information, and treatment decisions.

Optum Market Clarity dataset

The Optum Market Clarity dataset includes de-identified, deterministically linked claims data integrated with Optum's Clinical EHR data. It is fully HIPAA-compliant and statistician-certified. Clinical data are combined with adjudicated medical and pharmacy claims from both Optum-affiliated and non-affiliated payers. The Market Clarity dataset links EHR data with historical, linked administrative claim data, pharmacy claims, physician claims, facility claims (with clinical information), medications prescribed and administered, diagnoses, procedures, and information derived from clinical notes using NLP. For this study, the subset of individuals with health plan enrollment data available will be used. Insurance coverage will include commercial, Medicaid, and Medicare.

Figure 4. Market Clarity Data**7.5 STUDY SIZE**

Using data for Market Clarity integrated claims and clinical EHR data from 01 Jan 2016 - 31 May 2022, 1,179,017 patients with fibrosing-ILD were identified. Among them, 34,299 adult patients had at least one claim for oxygen therapy with 6 months of continuous enrollment in claims and 6 months of continuous activity in EHR.

These counts are for informational purposes only and may not reflect the final sample size. Application of other inclusion and exclusion criteria required for this study or other factors may reduce the sample size.

Table 3. Feasibility Counts from Market Clarity

Criteria	N

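### Letting statistical significance help choose the Cox covariates, then reporting ordinary HRs, CIs and p-values for the retained ones only, overstates weak or rare factors for oxygen initiation

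*Combined protocol and SAP*

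**What the plan says.** Section 7.6.1.3 (repeated in the Abstract) gives the purpose of the model: "Cox proportional hazards regression will be used to identify factors associated with initiation of oxygen therapy". This serves the second Aim 1 objective in Section 6, so the covariate hazard ratios are findings and not background adjustment.

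Entry to the model is governed by one sentence: "Covariates included in the adjusted model will be determined based on statistical significance and clinical rationale". The candidate list is open ("Baseline covariates may include"), with 6 demographic and 9 clinical items named. The reporting rule is: "Hazard ratios and associated 95% CIs and p-values will be reported for all covariates in the model".

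The section gives no significance threshold, no selection procedure and no set of covariates to be kept regardless. It does not say which criterion prevails when significance and clinical rationale disagree. It plans no holdout sample, bootstrap, shrinkage or multiplicity adjustment. The planned diagnostics cover fit and "violations of model assumptions (e.g. multicollinearity, non-proportionality"; selection is not among the examples. Annex 1 lists no stand-alone document that could supply the rule.

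**The concern.** Selection and inference use the same data. When a factor stays in the model because its estimate happened to be large relative to its standard error, the estimate reported for it is biased away from HR 1. The usual interval and p-value ignore that step. Candidates that fell out are not reported, so the reader cannot see how many were tried.

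The candidate pool is large. Section 7.3.5.2 expands the respiratory item into 10 separate indicators ("The following conditions will be included: pulmonary hypertension, acute respiratory failure, asthma, COPD, pneumonia, lung transplantation, upper respiratory tract infection", and three more). For the AHRQ item it says "The top 20 comorbid conditions will be presented". Counting only these two expansions, the 15 named items become 15 − 2 + 10 + 20 = 43 candidates. Some of them, such as lung transplantation and cystic fibrosis, could well be rare. At stake is a published list of factors associated with oxygen initiation in which the weaker entries look stronger and more precise than they are.

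**Working it through.** The plan states no threshold, event target or power for this model, so there is no figure of its own to reproduce. The size below rests on assumptions: selection at two-sided p<0.05 (c = 1.96), 1,000 to 34,299 events, and a binary factor with prevalence p of 50%, 10% or 2%.

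**1. Effect of selection on one factor.** Let m be the true log HR divided by its standard error, and let Z ~ N(m, 1) be the observed ratio. The factor is kept if |Z| > c.

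- P(keep) = 1 − Φ(c − m) + Φ(−c − m)
- E[Z | keep] = m + [φ(c − m) − φ(c + m)] / P(keep)
- Coverage given keep = Pr(|Z − m| < c and |Z| > c) / P(keep)

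For m = 1:
- P(keep) = 0.1685 + 0.0015 = 0.170
- Inflation = [1 + (0.2517 − 0.0050)/0.170] / 1 = 2.45
- Coverage = (0.975 − 0.8315)/0.170 = 0.1435/0.170 = 84%

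For m = 2:
- P(keep) = 0.516
- Inflation = [2 + (0.3986 − 0.0002)/0.516] / 2 = 2.772/2 = 1.39
- Coverage = 0.491/0.516 = 95.1%

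Coverage is 96.5% at m = 2.5 and 97.1% at m = 3. Under-coverage is therefore confined to m below about 2.

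**2. On the hazard-ratio scale.** SE = 1/√(events × p × (1 − p)). For example, 1,000 events and p = 10% give SE = 1/√90 = 0.105, so a true HR of 1.10 has m = 0.0953/0.105 ≈ 0.90. The mean HR when kept is the exponential of the mean log HR.

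| Events | Prevalence | True HR | Kept | Mean HR when kept | Coverage |
|---|---|---|---|---|---|
| 1,000 | 10% | 1.10 | 15% | 1.29 | 82% |
| 5,000 | 2% | 1.10 | 16% | 1.28 | 83% |
| 20,000 | 2% | 1.05 | 16% | 1.13 | 84% |
| 34,299 | 2% | 1.05 | 24% | 1.10 | 90% |
| 5,000 | 10% | 1.25 | 99.7% | 1.251 | 95% |
| 20,000 | 50% | 1.10 | 100% | 1.100 | 95% |

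The last two rows show that strong or common factors are barely affected.

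**3. Null candidates.** If the null candidates are independent, the chance that at least one is kept is 1 − 0.95^15 = 54% for 15 of them and 1 − 0.95^40 = 87% for 40.

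**4. What a full model changes.** A proportional-hazards simulation used 40 correlated binary candidates: 5 with HR 1.25, 10 with HR 1.07 and 25 null. Keeping all 40 gave average coverage of 94.5% at about 1,150 events and 95.5% at about 5,700. After backward elimination at p<0.05, coverage over the retained factors was 70% and 84%. That contrast sets a complete table against a selected one.

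A like-for-like contrast compares factors that are significant in the full model with those retained by elimination. In a linear-model analogue the coverages were 72% against 69% (n = 1,150), 83% against 81% (n = 5,700) and 88% against 88% (n = 20,000). The gain from the full model comes from reporting every factor, not from better estimates for the significant ones.

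**The case against.** The strongest reply is that the plan does not describe a pure p-value filter. Clinical rationale is also a criterion, and a factor kept on that ground is not selected on its p-value. This is correct. A reader might infer a stepwise procedure at p<0.05, but no such procedure or cut is stated. It does not dispose of the point, because the plan names no factor as kept on clinical grounds and does not say which criterion decides.

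The second reply is size. With 20,000 to 34,299 events and 10% prevalence, one standard error corresponds to an HR of only about 1.02 and two to about 1.04 to 1.05, so the distortion falls on effects of little interest. That also stands as far as it goes, but the number of Aim 1 events is not given. The feasibility statement in Section 7.5 ("34,299 adult patients had at least one claim for oxygen therapy with 6 months of continuous enrollment in claims") cannot stand in for it. That count accepts a single diagnosis, uses 6-month windows and does not exclude people with oxygen use before diagnosis.

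The third reply is that conditioning on significance harms a full model equally: any null factor with p<0.05 has a CI that excludes 1, whichever model produced it. This is right, and it limits what the fix can claim.

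Two further inferences are tempting but unsupported. A reader might think that the IPF subgroup is hit hardest because it is smaller. The documents give no IPF or non-IPF counts, and Section 7.6.1.3 does not say that the Cox model is fitted by cohort. A reader might also say that selection drops confounders. The model defines no exposure contrast, so no covariate is a confounder of a named effect.

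**Conclusion.** The point holds at moderate weight. The rule produces a table of selected estimates whose ordinary CIs and p-values do not account for the selection, and that table is an Aim 1 result. Under an assumed p<0.05 cut the distortion is material for factors whose true effect is below about two standard errors: 2.45-fold on the log HR with 84% coverage at one standard error. It is negligible for strong or common factors. Rare indicators can be affected even at 20,000 events. If events run to tens of thousands, little else is.

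The documents do not support reading this as invalidating the whole Cox table. Nor does the point reach the Aim 2 comparison of oxygen with no oxygen, because this model is associational and belongs to Aim 1. The threshold, prevalences and event counts used here are assumptions.

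**What to change.** In Section 7.6.1.3 and the matching Abstract text, replace the selection sentence with one full Cox model. Fix its covariate list on clinical grounds before outcomes are seen, use no significance-based selection, and report every covariate whether significant or not.

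The list should be the items now in Section 7.6.1.3 plus underlying ILD type and the other clinical characteristics (reflux disease, heart failure, sleep apnea). The Abstract names both groups as Aim 1 baseline covariates, but Section 7.6.1.3 leaves them out. Section 7.3.5.2 classifies underlying ILD type from claims over the entire study period, so its measurement window should be settled when it is added. Overlapping items, for example costs and HCRU, should be merged by a rule fixed in advance.

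The text should also say that factors highlighted because they are significant may still be exaggerated, since the full model does not remove that. If the team prefers to keep selection, it should prespecify the procedure and threshold and report bootstrap or penalised estimates with selection frequencies.

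The cost is a few sentences of wording, a longer results table and slightly wider intervals. No new data are needed.

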Age/age groups	X		X		X	
Race/ethnicity	X		X		X	
Sex	X		X		X	
Insurance type	X		X		X	
Geographic region	X		X		X	
Clinical characteristics						
Underlying ILD type‡	X		X		X	
Respiratory diseases	X		X		X	
Smoking	X		X		X	
Quan-Charlson comorbidity score	X		X		X	
AHRQ comorbid conditions	X		X		X	
Smoking	X		X		X	
Pulmonary rehabilitation	X		X		X	
Healthcare utilization characteristics						
Provider specialty	X		X		X	
Medication use	X		X		X	
All-cause HCRU and costs	X		X		X	

*As available among the subset of patients with information from both EHR and claims

†Measured as of the index date, or first available claim after the index date with value values for each of the characteristics

‡Measured using claims from the entire study period

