7.3.5.1 Demographic Characteristics

- **Index year**—The year of the patient’s fibrosing ILD diagnosis date or index date will be identified.
- **Age**—Age will be defined as of the index year.
- **Age groups**—Patients will be assigned to one of the following age groups: 18–44, 45–64, and 65+.
- **Sex**—Sex will be captured from enrollment data; patients with undefined gender will be removed from the study sample
- **Race/ethnicity**—Patients will be classified as Hispanic, non-Hispanic White, non-Hispanic Black, non-Hispanic Asian, Other/Unknown. This variable depends on the

availability of data within the sociodemographic data and will be missing for some patients.

- **Insurance type**—Payer type will be defined as commercial, Medicare, Medicaid.
- **Geographic region**—The U.S. region in which the patient is enrolled in a health plan will be described. States will be categorized into geographic regions in accordance with the U.S. Census Bureau's region designations. The five health plan regions are presented in Table 2.

Table 2. Health Plan Regions

Region	State
Northeast	CT, MA, ME, NH, RI, VT, NJ, NY, PA
Midwest	IL, IN, MI, OH, WI, IA, KS, MN, MO, ND, NE, SD
South	DC, DE, FL, GA, MD, NC, SC, VA, WV, AL, KY, MS, TN, AR, LA, OK, TX
West	AZ, CO, ID, MT, NM, NV, UT, WY, AK, CA, HI, OR, WA
Other	Armed Forces, American Samoa, Federated State of Micronesia, Guam, Marshall Islands, Commonwealth of the Northern Mariana Islands, Puerto Rico, Palau, Virgin Islands

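### The Aim 1 Cox model offers age only as three groups with an open top level from 65, which can leave modest residual confounding by age

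*Combined protocol and SAP*

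**What the plan says.** Section 7.6.1.3 states the purpose of the model: "Cox proportional hazards regression will be used to identify factors associated with initiation of oxygen therapy". The demographic candidates are "index year, age group, gender, race/ethnicity, insurance type, geographic region", and the abstract's data analysis entry repeats them. The list is introduced by "Baseline covariates may include", and the selection rule is "Covariates included in the adjusted model will be determined based on statistical significance and clinical rationale". A hazard ratio, confidence interval and p-value are to be reported for every covariate retained.

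Section 7.3.5.1 defines the groups: "Patients will be assigned to one of the following age groups: 18–44, 45–64, and 65", with a plus sign after the last figure, so the top group is open. The same section defines ungrouped age as a separate variable: "Age will be defined as of the index year". Table 1 in Section 7.3 carries both forms in one row, "Age/age groups", for both baseline periods. The variables entry of the abstract lists plain age, not age group, among the baseline covariates for Aim 1 and for Aim 2.

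The public text plans no continuous age term, no spline, no finer bands above 65 and no sensitivity analysis on how age is coded.

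**The concern.** With the groups "18–44, 45–64, and 65" and over, the age term gives every patient from 65 upward the same contribution to the hazard. Any real age gradient within that range has to go elsewhere. It can load onto covariates that vary with age, and several candidates plausibly do: insurance type (Medicare is one of three payer types), the Quan-Charlson score, comorbid conditions, utilization and costs.

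This matters because the model has no single exposure with the other terms as background. Its aim is to find factors associated with initiation, so each coefficient is a result. Covariates are also chosen partly by statistical significance. In a large claims sample, a small bias in an age-related covariate can be enough for it to be selected and reported as a factor. The analysis would also show nothing about how initiation changes with age above 65.

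**Working it through.** **Plan figures.** The plan gives no sample size, power or effect size for this model, so there is no figure of its own to reproduce. It gives no age distribution and no association between age and initiation. The bias can therefore only be illustrated.

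**Inputs from the documents.** The three age groups (7.3.5.1), age group as the model candidate (7.6.1.3), and a maximum Aim 1 follow-up of 5.75 years (01 October 2016 to 30 June 2022, Section 7.1).

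**Assumed inputs.**
- Age is normal with mean 68 and SD 12, or mean 72 and SD 10, truncated to 18–89.
- The initiation hazard is 0.2 per year at age 70 and log-linear in age, with a hazard ratio per 10 years of 1.0, 1.1, 1.25 or 1.5.
- One binary covariate has no true effect on initiation (true HR 1.00) and an odds ratio with age of 1.3 or 1.8 per 10 years.
- Censoring is exponential with mean 3 years, cut at 5.75 years. There is no competing death.
- There is one data set of 200,000 patients per scenario.

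Under these inputs 58% (mean 68) or 75% (mean 72) of patients fall in the top group, where the SD of age is about 6 years.

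**Result 1: hazard ratio of the null covariate.** The last column is the share of age confounding left by the three groups:

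(ln HR groups − ln HR continuous) / (ln HR no age − ln HR continuous)

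| Age mean/SD | HR per 10 y | OR per 10 y | No age term | Three groups | Continuous age | Share left |
|---|---|---|---|---|---|---|
| 68/12 | 1.1 | 1.3 | 1.037 | 1.014 | 1.004 | 0.31 |
| 68/12 | 1.1 | 1.8 | 1.064 | 1.020 | 1.003 | 0.29 |
| 68/12 | 1.25 | 1.3 | 1.059 | 1.009 | 0.990 | 0.29 |
| 68/12 | 1.25 | 1.8 | 1.146 | 1.043 | 0.998 | 0.32 |
| 68/12 | 1.5 | 1.3 | 1.128 | 1.043 | 1.005 | 0.32 |
| 68/12 | 1.5 | 1.8 | 1.262 | 1.077 | 0.993 | 0.34 |
| 72/10 | 1.1 | 1.3 | 1.017 | 1.006 | 0.998 | 0.41 |
| 72/10 | 1.1 | 1.8 | 1.061 | 1.037 | 1.018 | 0.45 |
| 72/10 | 1.25 | 1.3 | 1.044 | 1.016 | 0.996 | 0.41 |
| 72/10 | 1.25 | 1.8 | 1.112 | 1.054 | 1.006 | 0.46 |
| 72/10 | 1.5 | 1.3 | 1.078 | 1.032 | 0.995 | 0.46 |
| 72/10 | 1.5 | 1.8 | 1.185 | 1.080 | 0.999 | 0.46 |

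The standard error of ln HR is about 0.008, so departures of the continuous fit from 1.00 are mostly simulation noise. Because both fits use the same data, the ratio of the grouped to the continuous HR is the cleaner measure. It runs from 1.006/0.998 = 1.01 to 1.077/0.993 = 1.08.

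**Result 2: no age effect.** With an HR per 10 years of 1.0, the three-group HR was 1.001 to 1.010 and the HR without any age term was 1.001 to 1.009. Both lie within noise of 1.00, so there is no bias.

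**Result 3: whether a bias of this size could pass for a finding.** For a covariate present in half the patients, SE(ln HR) ≈ 2/√events, and z = ln HR / SE. The number of events is not known. Table 3 in Section 7.5 ends at 34,299 patients with oxygen evidence, under different criteria from those of this model, so that count serves only as the top of a range.

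| Spurious HR | 34,299 events | 10,000 events | 5,000 events |
|---|---|---|---|
| 1.05 (ln = 0.0488) | 4.5 | 2.4 | 1.7 |
| 1.08 (ln = 0.0770) | 7.1 | 3.9 | 2.7 |

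At a spurious HR of 1.01 (ln = 0.00995), z is 0.9 even with 34,299 events.

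**The case against.** **The list is not a fixed model.** This is correct. The covariates are ones the model may include, and the abstract names plain age elsewhere, so the form of age is not settled. But age group is the only form offered where the model is described, in both Section 7.6.1.3 and its abstract counterpart. The abstract's plain age does not say how age enters the regression. The point stands as a gap in specification.

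**The bias is small and the aim is descriptive.** This is largely fair. The three groups remove more than half of the age confounding in every scenario, and no single causal contrast is estimated. It lowers the priority without removing the point, because the coefficients are themselves the output and are partly chosen by significance.

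**The planned diagnostics would catch it.** Only in part. The examples given are fit, collinearity and proportionality of hazards, with corrections to follow. Functional form is not named, and a check on the grouped variable alone cannot show a gradient inside the top group.

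**Stronger readings that the documents do not support.**
- A reader might infer that the hazard ratios are wrong by a factor of 1.5 to 2.7. If the hazard rose 2% to 5% per year (an assumption), patients aged 66 and 86 would differ by 1.02^20 = 1.49 to 1.05^20 = 2.65. That is a contrast between two patients 20 years apart, not the bias in any reported hazard ratio.
- A reader might infer that the propensity score, and so the Aim 2 mortality comparison, inherits the grouping. Section 7.2.3 refers to Section 7.6.2.2 for the matching, and that section is not in the public text. The visible Aim 2 covariate list says age, not age group.
- A reader might take it as established that insurance type and comorbidity absorb the age differences. The documents give no age distribution, no payer mix above 65 and no effect of age on initiation, so this is conditional.

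**Conclusion.** The point holds for the Aim 1 Cox model only. Its covariate list offers age in three groups with an open level from 65, while ungrouped age (as of the index year) is defined in the same protocol. If age affects initiation, the grouping hides the gradient above 65 and leaves some age confounding in the hazard ratios of age-related covariates. Under the assumed inputs about 29% to 46% of the confounding remains, and a null covariate's hazard ratio moves to about 1.01 to 1.08. These figures depend on the assumed age distribution, a log-linear age effect and the assumed link between covariate and age. The real size cannot be derived from the documents and is nil if age has no effect. This is a cheap improvement to the specification and does not threaten the study's conclusions.

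**What to change.** In Section 7.6.1.3 and the matching abstract text, replace age group with age as a continuous variable, for example a restricted cubic spline, and report hazard ratios at a few chosen ages. Keep the three groups for descriptive tables only. This also brings the model list into line with the abstract's covariate list.

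The cost is a change of wording, since the variable is already defined and taken from claims. The one drawback is a slightly less simple presentation of the age effect than two group hazard ratios, which reporting at chosen ages largely offsets.
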